4.2. Safety Analyses

Safety data will be summarized by tumor type cohorts. Table 3 summarizes the safety analyses to be performed for all tumor type cohorts.

Adverse events (AEs) will be coded in accordance with the Medical Dictionary for Regulatory Activities (MedDRA). Severity of AEs will be graded by the investigator according to the NCI-CTCAE v4.03.

All laboratory values will be converted to and reported as international standard (SI) units. In general, only data from the central laboratory will be summarized and analyzed. Laboratory parameters will be graded using the NCI CTCAE v4.03.

Unless otherwise specified, only baseline and post-baseline values collected during the treatment-emergent period will be included in the safety analysis. In general, the treatment-emergent period is defined as the period from the date of the first dose of study treatment up to 30 days after last dose of ibrutinib or 90 days after last dose of durvalumab, whichever occurs later, or the day before initiation of subsequent antineoplastic therapy.

The treatment-emergent adverse events (TEAEs) are those events that occur or worsen during the treatment-emergent period or that are related to the study treatment. Safety data include subject disposition/ study status, demographics, baseline characteristics and baseline disease characteristics, study drug and treatment exposure, treatment discontinuation and study exit including primary reason, duration of treatment, TEAEs of grade 3 and above, serious TEAEs, TEAEs of major hemorrhage, TEAEs leading to any study treatment discontinuation, survival status, and death listings.

Table 3: Summary of Safety Analyses

Safety Assessment	Definition	Analysis Methods
Safety and tolerability	
AE: TEAEs, SAEs, grade 3 or worse TEAEs, related TEAEs, TEAEs leading to treatment discontinuation, TEAEs leading to dose reduction, TEAEs leading to death, protocol- defined events of special interest, and other safety observations
 
Worst post-baseline toxicity grade for selected lab tests: Worst post-baseline toxicity grade, Hgb, creatinine clearance, abnormal uric acid, liver function abnormalities
 
Vital signs, blood pressure, heart rate, temperature, respiratory rate, weight
	Descriptive summary statistics and/or listings

AE: adverse event; SAE: serious adverse event; TEAE: treatment-emergent adverse event

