## 7.1.2. **Laboratory**

Local laboratories will be used except for certain biomarker assays and in cases where a specialized laboratory is needed.

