### 7.1.2.1. **Hematology**

Hematology parameters will be performed at the site's local laboratory and will include a complete blood count: white blood cells, red blood cells, hemoglobin, hematocrit, platelets, neutrophils, lymphocytes, monocytes, eosinophils, basophils and bands (if reported).

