### 7.1.2.2. **Chemistry (Serum)**

Serum chemistry parameters will be performed at the site's local laboratory and will include sodium, potassium, chloride, blood urea nitrogen (BUN), creatinine, glucose, calcium, total protein, albumin, AST, ALT, alkaline phosphatase, total bilirubin, LDH, phosphate, uric acid, magnesium and bicarbonate. Amylase and lipase should be obtained at Screening, and any time during the study if clinically indicated for evaluation of pancreatitis.

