### 7.1.2.6. **Creatinine Clearance**

Creatinine clearance will be measured at the site's local laboratory and calculated using the Cockcroft-Gault method or determined by 24-hour creatinine clearance collection.

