### **10.6.1. Phase 1b Analyses**

The primary objective of Phase 1b is to determine the RP2D or MTD and to evaluate safety and tolerability of ibrutinib in combination with MEDI4736. An algorithm-based 6+3 dose de-escalation design is used to find the RP2D of the combination regimen and to characterize the most frequent adverse events and DLTs. DLTs will be evaluated and will include all AEs

experienced through Phase 1b. Study-drug exposure and laboratory data will be evaluated and summarized by dose cohort and tumor type.

The secondary objectives are to evaluate efficacy and pharmacokinetics / pharmacodynamics in subjects receiving the combination regimen. The ORR along with the corresponding 95% confidence interval based on exact binomial distribution and DOR for responders will be calculated and summarized with descriptive statistics by dose cohort and tumor type. Disease control rate (DCR) at Week 20 (Cycle 5) along with its 95% confidence interval based on exact binomial distribution will be provided by dose cohort and tumor type. Pharmacokinetics and pharmacodynamics data will be summarized by dose cohort and tumor type.

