#### **10.7.2. Clinical Laboratory Tests**

Laboratory tests will be summarized separately for hematology and serum chemistry. Local laboratory results will be converted based on the normal ranges and standardized using the International System (SI) unit. Selected hematology and chemistry laboratory parameters are detailed in [Section 7.1.2](#). Laboratory values will be graded using the [CTCAE v4.03](#).

Descriptive statistics will be provided for the values of selected clinical laboratory tests at each scheduled on-treatment evaluation including the final value. Percent change from baseline to each scheduled on-treatment evaluation and to the final value will also be summarized.

For selected variables, the mean value and mean percent change over time will be presented graphically.

A summary of the shifts in selected laboratory hematology and serum chemistry parameters from baseline to the worst toxicity grade during the study will be provided. The worst toxicity grade during the study will be tabulated.

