1. INTRODUCTION

This statistical analysis plan (SAP) lays out key elements including definitions and statistical methods for analysis of data in evaluation of efficacy and safety for the PCYC-1135-CA study. Analyses of pharmacokinetics data and biomarkers will be addressed in separate documents.

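### SAP 4.2 restricts laboratory summaries to central-laboratory data, but the protocol sends every safety laboratory test to local laboratories

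*SAP*

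**What the plan says.** SAP 4.2 says of laboratory values: "In general, only data from the central laboratory will be summarized and analyzed". SAP Table 3 then asks for the worst post-baseline toxicity grade on selected tests and names hemoglobin, creatinine clearance, uric acid and liver function.

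The general rule in Protocol 7.1.2 is the opposite: "Local laboratories will be used except for certain biomarker assays and in cases where a specialized laboratory is needed". Its subsections repeat this test by test. Hematology is done at the site's "local laboratory and will include a complete blood count: white blood cells, red blood cells, hemoglobin". Serum chemistry is done at the site's "local laboratory and will include sodium, potassium, chloride, blood urea nitrogen (BUN), creatinine, glucose, calcium, total protein, albumin, AST, ALT", and the same list goes on to alkaline phosphatase, total bilirubin and uric acid. Creatinine clearance is measured at the site's "local laboratory and calculated using the Cockcroft-Gault method or determined by 24-hour creatinine clearance collection".

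The protocol's analysis section follows the same source. Protocol 10.7.2 says: "Local laboratory results will be converted based on the normal ranges and standardized using the International System (SI) unit". It then plans descriptive statistics, percent change from baseline, shifts from baseline to worst grade, and a tabulation of worst grade. For Phase 1b, Protocol 10.6.1 adds: "Study-drug exposure and laboratory data will be evaluated and summarized by dose cohort and tumor type".

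SAP section 1 limits its own scope: "Analyses of pharmacokinetics data and biomarkers will be addressed in separate documents".

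**The concern.** A SAP should identify the data that feed each table. Here it names a source that the protocol does not create for safety tests. A programmer who applies the SAP rule literally would have nothing to tabulate for the laboratory part of Table 3 or for the shift tables in Protocol 10.7.2. A programmer who uses local data instead would be departing from the SAP without documentation.

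These tables have a purpose of their own. Safety and tolerability is a primary endpoint of Phase 1b, and clinical laboratory tests are one of the three safety assessments in SAP 1.2. Adverse event tables do not replace them, because under Protocol 7.1.1.5 a laboratory abnormality becomes an adverse event only when the investigator judges it clinically significant. Graded laboratory summaries can show changes that never reach the adverse event form. Protocol 1.4.5 states that there are no clinical data on this combination in the tumor types studied.

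**Working it through.** No arithmetic beyond counting applies. The check matches each laboratory item to the laboratory the protocol assigns, then looks for anything that could reconcile the two documents.

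**Step 1. Items named in SAP Table 3.**

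| Item | Protocol section | Laboratory |
|---|---|---|
| Hemoglobin | 7.1.2.1 | local |
| Uric acid | 7.1.2.2 | local |
| Liver function (AST, ALT, alkaline phosphatase, bilirubin) | 7.1.2.2 | local |
| Creatinine clearance | 7.1.2.6 | local |

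Local: 4 of 4. Central: 0 of 4.

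**Step 2. All test groups in Protocol 7.1.2.** Hematology, chemistry, TSH, coagulation, tumor markers, creatinine clearance, hepatitis serologies, urinalysis and the screening pregnancy test are each stated to be local. Local: 9 of 9. Central: 0 of 9.

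**Step 3. Could the protocol's exceptions supply central data?** Protocol 7.1.2 exempts certain biomarker assays and cases that need a specialized laboratory. Neither exception names a Table 3 item. The SAP sends biomarker and pharmacokinetic analyses to separate documents, so those samples are not what SAP 4.2 is about.

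**Step 4. Was a central laboratory introduced elsewhere?** The only facility the protocol calls central is an optional imaging vendor (7.1.3.2.1). The laboratory flowchart cited in Appendix 3 belongs to the pharmacokinetic, pharmacodynamic and biomarker schedule. SAP section 5 lists two changes, a pooled analysis across tumor cohorts and a change of terminology. Neither concerns the laboratory source.

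**Step 5. Can the opening qualifier resolve it?** It would have to exempt every safety laboratory item within the SAP's scope. No exception is written down.

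**Side check on creatinine clearance.** Protocol 8.1.1 and Appendices 1 and 2 schedule it once, at screening, with no assessment after baseline. SAP Table 3 nevertheless lists it under worst post-baseline grade and gives no derivation. Protocol 7.1.2.6 accepts either a Cockcroft-Gault calculation or a 24-hour collection, so the screening and later values could come from different methods.

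**The case against.** The strongest reply is that this is leftover wording with no practical effect. The SAP sentence is qualified, only one usable set of laboratory results exists, and Protocol 10.7.2 already gives the source, the unit conversion, the grading and the tables. With no second dataset to choose from, there is no room for selective reporting. The output is descriptive, and Protocol 10.7 plans no formal testing. Section 5 of the SAP introduces its list as the major change, so silence there proves little. The counts are counts of headings, not effects, and several of the nine groups (such as coagulation and hepatitis serologies) would not appear in these tables anyway. A replacement sentence naming local results might also seem to shut out a specialized laboratory.

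Much of this bears on weight, and it is right that local data are the probable intent. It does not remove the conflict: the SAP states a rule that the protocol cannot satisfy and gives no exception. The count of four is the relevant one; the count of nine only confirms that nothing else was overlooked. The replacement sentence below does not say that only local results count, so it does not exclude a specialized laboratory. The creatinine clearance point is a separate gap in detail, and the main conclusion does not depend on it.

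**Conclusion.** The concern holds. SAP 4.2 contradicts Protocol 7.1.2 and 10.7.2 on the source of laboratory data. Taken at its word, it retains no data for any of the four named Table 3 items or for the planned shift tables. This is a rule that is wrong as written, not a missing detail.

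The consequence is limited to the descriptive laboratory safety summaries, including those by dose cohort and tumor type in Phase 1b. Decisions on dose-limiting toxicity and the recommended Phase 2 dose (Protocol 5.2 and 5.3), reporting of adverse events and events of special interest, and the overall response rate do not depend on the sentence.

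The conclusion assumes that no central safety laboratory was adopted outside these two documents. If one was, the protocol text is out of date and the change is undocumented, so a correction is still needed. The sentence should be corrected before the laboratory tables are programmed.

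**What to change.** Replace the sentence in SAP 4.2 with:

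> Local laboratory results, converted and standardized as described in Protocol 10.7.2, will be summarized and graded per NCI CTCAE v4.03.

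If a central laboratory was in fact adopted, amend Protocol 7.1.2 and 10.7.2 instead, and list the change in SAP section 5.

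For creatinine clearance, either drop it from the post-baseline items in SAP Table 3 or add:

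> Baseline and post-baseline creatinine clearance will both be derived by the Cockcroft-Gault method from local serum creatinine, weight, age and sex.

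Using one method at both times avoids comparing a 24-hour collection at screening with a calculated value later.

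The cost is one replaced sentence and one added line. Hematology, serum chemistry and weight are already scheduled on treatment in Appendices 1 and 2, and demographics are taken at screening, so no new visits or samples are needed.

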#### **1.4.4.6. Other Malignancies**

Other malignancies, most frequently skin cancers, have occurred in subjects treated with ibrutinib. Other malignancies including non-skin carcinomas have occurred in patients treated with ibrutinib. The most frequent second primary malignancy was non-melanoma skin cancer.

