### **8.3.4. Survival Follow-up**

Once subjects progress or start use of alternative anticancer therapy (for subjects who have not withdrawn consent), they will be contacted approximately every 12 weeks ( $\pm 7$  days) from the last dose by clinic visit or telephone to follow up on survival and use of alternative anticancer therapy (including the response and disease progression for the therapy), up to 3 years after the

first dose of the last subject enrolled. Subjects will be contacted until death, subject withdrawal, lost to follow-up, or study termination by the Sponsor, whichever occurs first.

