#### **11.4.5. Other Malignancies**

All new malignant tumors including solid tumors, skin malignancies and hematologic malignancies will be reported for the duration of study treatment and during any protocol-specified follow-up periods including post-progression follow-up for overall survival. Other malignancies will only be reported as an SAE if the event meets any serious adverse event reporting requirement listed under section "Serious Adverse Event" (otherwise captured as an AE in the eCRF).

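### The SAP plans no analysis of other malignancies over the period in which the protocol collects them, so late ones judged unrelated have no assured place in the results

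*SAP*

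**What the plan says.** **The risk.** Protocol 1.4.4.6, under the ibrutinib risks, states: "Other malignancies, most frequently skin cancers, have occurred in subjects treated with ibrutinib". It adds that non-skin carcinomas have also occurred and that non-melanoma skin cancer was the most frequent second primary.

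**Collection.** Protocol 11.4.5 says that all new malignant tumors "will be reported for the duration of study treatment and during any protocol-specified follow-up periods including post-progression follow-up for overall survival". It sets no causality condition. On the route of reporting it says: "Other malignancies will only be reported as an SAE if the event meets any serious adverse event reporting requirement". Other cases are captured as AEs in the eCRF.

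**Survival follow-up.** Protocol 8.3.4 sets a contact about every 12 weeks, up to 3 years after the last enrolled subject's first dose: "Subjects will be contacted until death, subject withdrawal, lost to follow-up, or study termination by the Sponsor, whichever occurs first". The stated purpose of the contact is "to follow up on survival and use of alternative anticancer therapy", with response and progression on that therapy. New malignancies are not mentioned.

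**Analysis.** SAP 4.2 opens its restriction with an unless-otherwise-specified proviso and then states that "only baseline and post-baseline values collected during the treatment-emergent period will be included in the safety analysis". The treatment-emergent period runs from first dose to the later of 30 days after ibrutinib and 90 days after durvalumab, or to the day before subsequent antineoplastic therapy. TEAEs are events that start or worsen in that period, or that are related to study treatment. Neither the text of SAP 4.2 nor its Table 3 names other malignancies. Major hemorrhage, by contrast, is named.

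**The concern.** The protocol treats second cancers differently from ordinary adverse events. It follows them past the usual 30/90-day limit, past progression and past the start of new therapy, and it does so without asking whether study drug was the cause. That only makes sense if the late events are going to be looked at. The SAP then applies its ordinary safety window and provides no separate output.

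At stake is the completeness of the report on a named risk. After the window closes, the one assured route into the results is the investigator's judgement that the event is related. In a single-arm trial that judgement is difficult once another anticancer drug has been given. A late cancer attributed elsewhere could be collected under 11.4.5 and then appear in no table or listing.

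**Working it through.** The plan gives no figure to reproduce, so the check is mainly a comparison of texts.

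**Step 1. Where a malignancy goes if it arises after the treatment-emergent period ends.**

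| Late event | Reported under Protocol 11.4.5 | Place in SAP 4.2 |
|---|---|---|
| Related to study treatment | Yes | TEAE, through the relatedness clause, with no time limit |
| Not related, serious | Yes | Ambiguous: Table 3 lists SAEs without a treatment-emergent prefix, while the text lists serious TEAEs |
| Not related, non-serious | Yes | None assured |

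**Step 2. Other routes into the results.**

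- *Events of special interest (Table 3).* Protocol 11.4.6 covers major hemorrhage, pneumonitis, hypersensitivity reactions and hepatic abnormalities. Other malignancies stand in a separate section, 11.4.5, so this entry does not bring them in.
- *Other safety observations (Table 3).* The term is undefined. It could cover late malignancies, but it commits nobody to reporting them.
- *The opening proviso of the restriction.* It would admit an exception, but the SAP specifies none for malignancies.
- *Death listings.* These could show a fatal case, but not a non-fatal one.
- *SAP section 5 (changes from the protocol).* It does not address the point.

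**Step 3. Whether the late events would be collected.** Protocol 11.4.5 requires it. Protocol 11.4.2 stops eCRF recording of non-serious AEs at 30/90 days, and after that asks for SAEs only if considered related. The AE row in Appendices 1 and 2 also stops at 30/90 days. The Survival FU entries list survival status, subsequent therapy and progression. A site working from the schedule could miss what 11.4.5 asks for.

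**Step 4. How much calendar time lies outside the window (illustration only).** The documents give no treatment duration, so the stop days are assumed. I is the last ibrutinib day, D the last durvalumab day (Day 15 of the last durvalumab cycle), and collection is taken as 3 × 365 = 1,095 days from first dose.

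Window end E = max(I + 30, D + 90). Share outside = (1,095 − E) / 1,095. If new therapy starts 30 days after the last ibrutinib dose, and this is read as cutting the period short, the end is min(E, I + 29).

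| Assumed stop | I | D | E | Share outside | End with new therapy | Share outside |
|---|---|---|---|---|---|---|
| Both, about end of Cycle 2 | 56 | 43 | max(86, 133) = 133 | 962/1,095 = 88% | 85 | 1,010/1,095 = 92% |
| Both, about end of Cycle 5 | 140 | 127 | max(170, 217) = 217 | 878/1,095 = 80% | 169 | 926/1,095 = 85% |
| Both, about 12 months | 364 | 351 | max(394, 441) = 441 | 654/1,095 = 60% | 393 | 702/1,095 = 64% |
| Durvalumab 12 months, ibrutinib 2 years | 728 | 351 | max(758, 441) = 758 | 337/1,095 = 31% | 757 | 338/1,095 = 31% |

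These shares (31% to 92%) apply to a subject followed for the full 1,095 days. Death or loss to follow-up before then lowers them. They measure calendar time, not missed events.

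**The case against.** The best defence is that the SAP is within its rights. Protocol 10.7.1 plans the analysis of treatment-emergent AEs and leaves their definition to the SAP. Protocol 11.4.5 is a reporting rule for investigators and prescribes no table. A reporting window wider than the analysis window is not in itself an error, and ending the main safety period at the next therapy is defensible in a single-arm trial. All of this stands. There is no undeclared departure from the protocol, and the TEAE window need not change.

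It can also be said that the quoted restriction speaks of values and directly follows the laboratory paragraph. That is fair, but the TEAE definition in the next paragraph applies the same window to events, with relatedness as the only exception.

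A reader might infer that later second cancers as a group are left out of the results. The documents do not support that. The restriction is a default, related events enter at any time, and late serious ones may enter through the SAE entry in Table 3.

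A reader might also infer a known downward bias in the malignancy incidence, or argue from long latency and a quick move to further therapy. The documents state no latency, no time to next therapy and no malignancy rate. An incidence confined to the treatment-emergent period is a legitimate, different quantity. It would mislead only if presented as the incidence over the whole study.

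Finally, the silence of 8.3.4 and the appendices might be called housekeeping, since 11.4.5 already creates the duty. That is partly so, but 11.4.2 and the AE rows give a conflicting stopping point, so the sections need reconciling.

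**Conclusion.** The point holds in a limited form. The protocol collects new malignancies through survival follow-up without regard to cause. The SAP's default window closes much earlier, later events are assured a place only if related, and no analysis of other malignancies is specified. Late malignancies judged unrelated have no assured place in the results, the non-serious ones most clearly. For late serious ones the SAP contradicts itself between its text and Table 3.

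The number of events affected cannot be derived, since treatment duration and malignancy rate are both missing. The illustration shows only that, under the assumed stop days and full 1,095-day follow-up, the time outside the window can be a large part of the collection time. Nothing here touches the primary endpoint, the decision rules or the error rates. It is an inexpensive improvement to the safety reporting and should be made.

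**What to change.** 1. Add to SAP 4.2 and Table 3 a summary and a listing of all other malignancies as collected under Protocol 11.4.5. They should run from first dose to end of follow-up, regardless of relationship to study treatment and of later antineoplastic therapy. Show events inside and outside the treatment-emergent period separately, and report follow-up time.
2. In the same place, state whether the SAE entry in Table 3 means all SAEs or serious TEAEs only.
3. Reconcile Protocol 8.3.4, 11.4.2 and the AE and Survival FU entries of Appendices 1 and 2 with 11.4.5, by adding a new-malignancy item to the existing 12-weekly survival contact.

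The cost is one table, one listing and one question at a contact that already takes place. No dose, treatment rule, endpoint or sample size changes. The downside is that some late events will reflect the next therapy rather than study treatment. The split by period makes that visible.

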#### **5.4. Study Treatment**

All eligible subjects will be treated with ibrutinib PO and MEDI4736 IV in 28-day cycles. On infusion days where pharmacokinetic, pharmacodynamic or biomarker samples are taken post dose, MEDI4736 IV should be given first, followed by that day's ibrutinib dose. Missed doses of ibrutinib and MEDI4736 will not be made up. Dose escalation of any agent (ibrutinib or MEDI4736) at any time will not be allowed. MEDI4736 will be given for a maximum of 12 months. Re-treatment with MEDI4736 will not be allowed following completion of 12 months of treatment, regardless of any dose delays or missed doses. Treatment with ibrutinib will continue for up to 3 years or until disease progression or unacceptable toxicity.

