#### **8.3.1. End-of-Treatment Visit for Ibrutinib**

An End-of-Treatment Visit should occur 30 days ( $\pm 7$  days) from the last dose of ibrutinib or prior to the start of a new anticancer treatment. *This visit may occur as a standard Day 1 cycle study visit if the subject continues treatment with MEDI4736 alone.* An optional tumor tissue biopsy may be collected if treatment was discontinued due to PD.

Subjects who withdraw consent to treatment may still have an End-of-Treatment Visit. The following procedures will be performed at the End-of-Treatment Visit:

- Complete physical exam
- ECOG Performance Status
- Vital signs and weight
- Clinical laboratory tests for:
  - Hematology
  - Serum chemistry
  - Disease-specific tumor markers
  - Pregnancy test

- Research laboratory blood samples collected:
  - Biomarkers and pharmacodynamics (unless taken within the last 7 days)
- Review of AEs and concomitant medications

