### **8.3.2. 90-day Follow-Up Visit for MEDI4736**

A 90-day Follow-Up Visit should occur approximately 90 days ( $\pm 7$  days) after the last dose of MEDI4736 or prior to the start of a new anticancer treatment. *This visit may occur as a standard Day 1 cycle study visit if the subject continues treatment with ibrutinib alone.* Subjects who withdraw consent to treatment may still have a 90-day Follow-Up Visit. The following procedures will be performed:

- Complete physical exam
- ECOG Performance Status
- Vital signs and weight
- Clinical laboratory tests for:
  - Hematology
  - Serum chemistry
  - Urinalysis
  - Disease-specific tumor markers
  - TSH
- Research laboratory blood samples collected:
  - Pharmacokinetics and pharmacodynamics
- Review of AEs and concomitant medications

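### The SAP safety window allows no visit tolerance, so laboratory and vital-sign values from a permitted but late 90-day visit (days 91 to 97) can fall outside the analysis

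*SAP*

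**What the plan says.** SAP 4.2 states that, unless otherwise specified, "only baseline and post-baseline values collected during the treatment-emergent period will be included in the safety analysis". It defines the end of that period as "up to 30 days after last dose of ibrutinib or 90 days after last dose of durvalumab, whichever occurs later". A new antineoplastic treatment also closes the period, on the preceding day. No visit tolerance is added, and no exception is written anywhere in the SAP.

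The protocol schedules two post-treatment safety visits, each with a tolerance of 7 days either way:

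- Protocol 8.3.1: "An End-of-Treatment Visit should occur 30 days" from the last ibrutinib dose, so days 23 to 37.
- Protocol 8.3.2: "A 90-day Follow-Up Visit should occur approximately 90 days" after the last durvalumab (MEDI4736) dose, so days 83 to 97.

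Either visit may be brought forward to precede a new anticancer treatment. Both include hematology, serum chemistry, vital signs and weight. The 90-day visit adds TSH and urinalysis.

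The two drugs need not stop together. Protocol 5.4 says that "MEDI4736 will be given for a maximum of 12 months", while ibrutinib may run for up to 3 years.

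**The concern.** For a subject off both drugs, the SAP window closes on the nominal day of the visit that supplies its last scheduled laboratory and vital-sign values. If the clinic books that visit two days before day 90, the values count. If it books the visit two days after, equally within protocol, they do not. Inclusion then depends on the appointment date rather than on anything about the subject.

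The output at stake is mainly the worst post-baseline grade in SAP Table 3, which names hemoglobin, creatinine clearance, uric acid and liver function, together with the vital-sign summaries. Leaving out a late value can only lower a worst grade or leave it unchanged. Hepatotoxicity and nephritis are among the durvalumab risks listed in protocol 1.5.3, and after the 90-day visit no further hematology or chemistry is scheduled for subjects off treatment.

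Protocol 10.7.2 describes laboratory shifts to the worst grade over the whole study. The SAP window is narrower, and SAP section 5 does not list this among its changes to the protocol.

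**Working it through.** The plan gives no figure on this point, so there is none to reproduce. The check is a count of days.

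**Inputs.** SAP 4.2: +30 days for ibrutinib, +90 days for durvalumab, the later of the two governs. Protocol 8.3.1: 30 ± 7 days. Protocol 8.3.2: 90 ± 7 days.

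**Set-up.** Let day 0 be the last durvalumab dose and g the number of days from the last durvalumab dose to the last ibrutinib dose. Assume no new antineoplastic therapy has started.

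- Window end: E = max(90, g + 30).
- 90-day visit, permitted days 83 to 97 (97 − 83 + 1 = 15 days). Days lost = max(0, 97 − E).
- End-of-Treatment visit, permitted days g + 23 to g + 37 (15 days). Days lost = max(0, g + 37 − E).

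**Results.**

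| g (days) | Window end E | 90-day visit: days lost of 15 | End-of-Treatment visit: days lost of 15 |
|---|---|---|---|
| 0 (stopped together) | 90 | 7 | 0 |
| 53 | 90 | 7 | 0 |
| 54 | 90 | 7 | 1 |
| 57 | 90 | 7 | 4 |
| 60 | 90 | 7 | 7 |
| 61 | 91 | 6 | 7 |
| 66 | 96 | 1 | 7 |
| 67 | 97 | 0 | 7 |
| 365 | 395 | 0 | 7 |

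Negative g (ibrutinib stopped first) gives the same result as g = 0. Both visits lose all 7 late days only at g = 60. A visit on or before its nominal day is never lost, because E is at least 90 and at least g + 30.

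**Share of visits.** This depends on when visits are actually held, which neither document reports. If all fall by the nominal day, the share lost is 0%. If they spread evenly over the 15 days, it is 7/15 = 47%.

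**With a 7-day allowance.** E becomes max(97, g + 37). Days lost are then max(0, 97 − E) = 0 and max(0, g + 37 − E) = 0 for every g.

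**The case against.** The case for leaving the SAP alone has several parts.

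- The 30- and 90-day limits match the protocol's adverse-event collection period (protocol 11.4.2), so one common window is defensible. That is a good reason to keep the adverse-event window. It is not a reason to apply the same limit to values from visits that the protocol allows later.
- The SAP hedges its rule as general and open to exceptions. The hedge has no effect, since no exception is written. The by-visit windows in SAP section 2 assign assessments to visit labels and do not lengthen the treatment-emergent period.
- Adverse events offer some cover. Treatment-related events count as treatment-emergent whatever their date, and related serious events remain reportable after the window. This stands, so no general loss of adverse events follows. It does not cover a non-serious abnormality first found on, say, day 95: routine recording has ended by then.
- The summaries are descriptive, and losing one visit is not the same as losing a worst grade. This stands and limits the importance.
- SAP 4.2 also says that, in general, only central-laboratory data are summarized, whereas protocol 7.1.2 uses local laboratories for routine tests. Read literally, that removes the routine results on day 83 as much as on day 97. This stands. It is a larger problem than the 7-day gap and must be settled for the fix to work on laboratory values.

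A reader might also infer that day 30 after ibrutinib is a cut-off for everyone. It is not, because the later date governs: with both drugs stopped together, the End-of-Treatment visit loses nothing. The relevant gap runs from the last durvalumab dose to the last ibrutinib dose, not to the visit.

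**Conclusion.** The mismatch is real and minor. When ibrutinib ended no more than 60 days after durvalumab, a compliant 90-day visit on days 91 to 97 contributes no laboratory or vital-sign values to the safety analysis. The loss falls by one day for each further day of gap and is zero from 67 days. The End-of-Treatment visit is affected only from a gap of 54 days, and fully from 60. Such gaps can arise because durvalumab is capped at 12 months and ibrutinib is not.

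Three stronger readings are not supported. Visits held on schedule are not lost in general; only the late part of the tolerance is affected. The 47% is not an estimate of lost visits, since it assumes even spread and the documents give no timing; visits brought forward for new therapy are unaffected by the 7-day gap. Under-counting of late endocrine effects in Table 3 cannot be claimed, because TSH is not among the tests named there.

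The conclusion assumes that the SAP window is applied as written and that new antineoplastic therapy, where started, closes it earlier.

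**What to change.** Add one sentence to SAP 4.2: visit-based laboratory and vital-sign values are included if collected up to 37 days after the last ibrutinib dose or 97 days after the last durvalumab dose, whichever is later, and before any subsequent antineoplastic therapy. Leave the adverse-event window at 30 and 90 days.

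In the same revision, reconcile the central-laboratory sentence in SAP 4.2 with the local laboratories in protocol 7.1.2. Without that, the change recovers only vital signs.

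The cost is the added sentence, the reconciliation and one programming constant. No new data are needed and patient management is unchanged. The drawback is that the laboratory and adverse-event windows will differ by 7 days, which a table footnote can state.
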